#### **Methodology:**

This is a clinical trial that will enroll approximately 100 subjects from three different research sites. Patients who have been diagnosed with cyclic vomiting syndrome and enrolled in our study will be given standard treatment of 2.5mg droperidol IV, 8mg ondansetron IV or 5mg haloperidol IM per physician's choice. The research specialist will be notified when the drugs are administered and view the patient's chart to determine if the reason for the anti-nausea drug was a diagnosis of cyclic vomiting syndrome. If so, the patient's nurse will be messaged via EPIC to inquire on the patient's pain and nausea scores initially versus two hours after the drug is administered, if at the St. Joseph ED, research specialist will make contact with the patient and ask pain/nausea scores at baseline and 2 hours later themselves.

Inclusion criteria will be adult patients with a clinical diagnosis of cyclic vomiting in the ED

Exclusion criteria would include pregnancy, allergy to any of the study medicines

Primary outcome will be change in pain and nausea at 2 hrs using a visual analog scale of 0-10

Secondary outcome will be:

1. Change in pain [ Time Frame: 1, 2, 24 and 48 hours ]

Changes in abdominal pain score at 1, 2, 24 and 48 hours vs. baseline

2. Change in nausea [ Time Frame: 1, 2, 24 and 48 hours ]

Changes in nausea score at 1, 2, 24 and 48 hours vs. baseline

3. Treatment success [ Time Frame: 2, 24 and 48 hours ]

Treatment success = both abdominal pain and nausea score < 2 at 2, 24 and 48 hours

4. Discharge ready at 2 hours [ Time Frame: 2 hours ]

Deemed discharge-ready at 2 hours in the opinion of the treating physician

5. Rescue anti-emetics in ED [ Time Frame: at discharge from Emergency Department or 12 hours whichever comes first ]

Given rescue anti-emetics prior to discharge

6. Time to discharge from ED [ Time Frame: at discharge from Emergency Department or 12 hours whichever comes first ]

Time interval to discharge-ready from t=0 (min)

Subject preferred Time to Discharge from ED" > 12 hours (binary yes/no)

7. Return to ED [ Time Frame: 7 days ]

Unscheduled return visits to ED within 7 days (count)

8. Prolonged ED Length of stay [ Time Frame: at discharge from Emergency Department or 12 hours whichever comes first ]

Outcome 10 "

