**Research Design:**

Patients presenting with a chief complaint of vomiting and abdominal pain will be screened by the bedside provider for the diagnosis of cyclic vomiting or cannabis induced vomiting syndrome. Per the doctor's choice, 2.5mg droperidol, 5mg haloperidol or 8mg odansteron will be administered. The remaining portion of the patients care is at the discretion of the treating provider including the use of fluids, laboratory diagnostics and radiographic diagnosis and pain medications. The research specialist will be notified when the drugs are administered and view the patient's chart to determine if the reason for the anti-nausea drug was a diagnosis of cyclic vomiting syndrome. If so, the patient's nurse will be messaged via EPIC to inquire on the patient's pain and nausea scores initially versus two hours after the drug is administered, if at the St. Joseph ED, research specialist will make contact with the patient and ask pain/nausea scores at baseline and 2 hours later themselves. Our research specialist will contact patients 1 and 2 days following treatment and enter responses into the project spreadsheet housed on Spectrum Health Lakeland servers. The provider may, at any time choose to add additional anti emetics at their choice but this will be considered as a "rescue" medication for the purposes of this study. All enrolled patients will be added to a study list where the medication given as well as the the secondary outcomes will be recorded on a secure spreadsheet for analysis later.

Continuous variables (such as pain and nausea score, length of stay in the ED will be analyzed using 2 tailed student t-tests. Qualitative variables (number with 2 point improvement in abd pain and nausea score, discharge state at 2 hours, need for rescue anti-emetic, return to ED) will be analyzed using chi-squared analysis.

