#### **Informed consent**

Patients experiencing cyclical vomiting exacerbations tend to be very symptomatic and are very uncomfortable. The HAVOC trial (Ruberto et al) experienced low enrollment due to patients not being able to participate in consent discussions. The medicines we are proposing to use are all medicines that have been effective for cyclic vomiting, but it is unknown if droperidol, a relatively recent re-addition to clinicians' pharmacologic armamentarium is better or worse than haloperidol. We feel that since clinicians are going to try droperidol for these patients anyway, we would like to formally assess its utility. We do not want to delay these patients' treatment to go over a lengthy consent document for medicines that will frequently be used in any case, and these patients will often not tolerate carrying this discussion out

**Statistical Analyses:** Means and standard deviations were reported for baseline pain and nausea and for pain and nausea after 2 hours of drug administration for the three arms of the study. ANOVAs were conducted to determine whether significant differences existed between baseline and 2 hours after drug administration for the three drugs. Due to low response rate at 24 and 48 hours (6 pts), these time points were not included in the analysis.

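### Time to discharge-ready (secondary outcome 6) falls under a t-test, with no rule for patients who are admitted or not ready at 12 hours, which tends to dilute a real difference in treatment failure

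*Combined protocol and SAP*

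**What the plan says.** The Methodology section lists secondary outcome 6, time to discharge from the ED, and measures it as "Time interval to discharge-ready from t=0 (min" in minutes. Its time frame is "at discharge from Emergency Department or 12 hours whichever comes first". Beside it stands a yes/no item for times above 12 hours, "12 hours (binary yes/no". Outcome 8 is a separate entry for prolonged ED stay.

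The analysis rule is in the last paragraph of Research Design: "Continuous variables (such as pain and nausea score, length of stay in the ED will be analyzed using 2 tailed student t-tests". The list is open-ended. It names length of stay, and time to discharge-ready comes under it as another continuous variable. The chi-squared list in the same paragraph covers discharge state at 2 hours, rescue anti-emetics and return to the ED, but not the over-12-hours item.

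The Statistical Analyses paragraph, placed under Informed consent, covers pain and nausea only: "ANOVAs were conducted to determine whether significant differences existed between baseline and 2 hours after drug administration for the three drugs". It describes no analysis of outcome 6.

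The documents do not say what value a patient takes who is admitted or is not discharge-ready at 12 hours. Censoring, competing events and time-to-event methods are not mentioned.

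**The concern.** A patient still in the ED at 12 hours has only a lower bound for the time to discharge-ready. A patient admitted to a ward may have no such time at all. A t-test cannot use either record as it stands. The analyst must leave the patient out or enter a number as if the patient had become ready then.

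These patients include many of the treatment failures, which the Problem and Purpose Statement lists among the things to be compared. Ethical Considerations names shorter stay as a hoped-for benefit. Admission is foreseeable, because the Introduction opens with the rise in hospitalizations for this condition. If one drug leads to more admissions, an analysis that drops those patients or uses their ward-transfer time loses most of that difference.

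**Working it through.** The plan states no power, alpha or sample-size derivation, so there is no planned figure to reproduce. The one related sum agrees: 5.6 − 3.1 = 2.5 h, as cited in Theoretical Framework-Present Knowledge.

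**1. The 12-hour limit alone**

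Inputs: cited ED departure times of 3.1 h (SD 1.7) for haloperidol and 5.6 h (SD 4.5) for ondansetron. These are departure times, used here as a stand-in for discharge-ready times. A lognormal shape is assumed.

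Formulas: σ² = ln(1 + (SD/mean)²); μ = ln(mean) − σ²/2; z = (ln 12 − μ)/σ; share beyond 12 h = 1 − Φ(z); A = mean × Φ(z − σ); capped mean = A + 12 × share; mean with long stays dropped = A/(1 − share).

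- Ondansetron: σ = 0.706, μ = 1.474, z = 1.433, share = 7.6%. A = 5.6 × 0.766 = 4.29. Capped mean = 4.29 + 12 × 0.076 = 5.20 h. Dropped mean = 4.29/0.924 = 4.64 h.
- Haloperidol: σ = 0.513, μ = 1.000, z = 2.896, share = 0.2%. A = 3.07. Capped mean = 3.10 h. Dropped mean = 3.08 h.
- Gap: 2.5 h uncapped; 5.20 − 3.10 = 2.1 h capped; 4.64 − 3.08 = about 1.6 h dropped.

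A gamma shape gives 9.0% and 0.04% beyond 12 h, with capped means of 5.23 and 3.10 h, so the capped gap is again about 2.1 h.

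**2. Admissions (hypothetical, because no rate is given)**

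Assumptions: discharge times identical in both arms among those sent home (lognormal, mean 3.5 h, SD 2.0, 12-hour capped mean 3.49 h); ward transfer at 3 to 6 h, midpoint 4.5 h; 10% admitted in one arm. With g the difference in admission rate:

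- admitted dropped: 0
- ED departure time used: g × (4.5 − 3.49)
- 12-hour restricted mean, admitted held as not ready: g × (12 − 3.49)

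| Admitted | Dropped (h) | ED departure (h) | Restricted mean (h) |
|---|---|---|---|
| 10% v 10% | 0 | 0 | 0 |
| 10% v 15% | 0 | 0.05 | 0.43 |
| 10% v 20% | 0 | 0.10 | 0.85 |
| 10% v 25% | 0 | 0.15 | 1.28 |
| 10% v 30% | 0 | 0.20 | 1.70 |

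**3. Rejection rates (simulation, 3,000 runs)**

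The plan is to "enroll approximately 100 subjects from three different research sites". About 33 per drug and two-sided 0.05 are assumed. Discharge times are identical in both arms (mean 3.1 h, SD 1.7), and admitted patients' departure times follow the same distribution. With 10% admitted against 20%, 30% and 40%:

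- t-test, admitted dropped: 4% to 5% throughout
- t-test, departure time used: about 5% throughout
- rank test, admitted held as not ready at 12 h: 10%, 29%, 55%
- t-test on those same held values: 17%, 48%, 78%

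At 10% v 10%, all four reject at about 4% to 5%. The last line shows that what recovers the difference is the rule for admitted patients.

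**The case against.** Several objections stand.

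- A reader might infer that the plan instructs analysts to drop failures or count them as discharges. It does not. Admission is never described as a disposition and the 12 hours appears only as a time frame. Dropping or assigning is what a t-test forces when no rule is given.
- "length of stay in the ED will be analyzed using 2 tailed student t-tests" names length of stay, which every patient who leaves the ED has, including those admitted. Time to discharge-ready is a different quantity and reaches the t-test only because the list is open-ended.
- A reader might infer that the drug with more failures would look better. The scenarios above do not show that. With transfer at 3 to 6 h, the arm with more admissions looks slightly slower. Reversal needs transfers earlier than the typical discharge, and the documents give no transfer times. Dilution is supported; reversal is not.
- The cap calculation concerns ondansetron, whereas the research question is droperidol against haloperidol. At haloperidol-like times the cap has almost no effect, and no droperidol times are given.
- The admission figures follow directly from the assumed rates, and vanish when the rates are equal.

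The over-12-hours item answers part of the concern, since it keeps long stays visible. It does not enter the t-test, has no named test, and misses patients admitted before 12 hours.

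**Conclusion.** The concern holds as a gap between the outcome and its test. Outcome 6 can be incomplete, the test assigned to continuous variables requires complete values, and no rule connects them. The tendency is to dilute a real difference in treatment failure.

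The cap alone takes about 0.4 h off a 2.5 h haloperidol-ondansetron gap, and dropping the long stays takes about 0.9 h off. Both rest on the cited departure times and an assumed lognormal shape. Unequal admission could matter more: up to 1.7 h at 10% v 30%, of which the t-test would show 0 to 0.2 h. That range is hypothetical and starts at zero.

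A 12-hour restricted mean is itself a capped mean, so it does not restore the 2.5 h. Its gain is that the limit is declared, the share not ready at 12 hours is shown, and admitted patients stay in the comparison.

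The documents do not support extending this to the main result. The outcome is secondary, the primary outcome is untouched, and the Statistical Analyses paragraph describes no analysis of outcome 6. The point should be corrected before any comparison on outcome 6 is reported.

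**What to change.** For outcome 6, replace the t-test with a time-to-event analysis over 12 hours that keeps every patient. Hold admitted patients as not discharge-ready to 12 hours (equivalently, treat admission as a competing event), and censor those still in the ED at 12 hours. Report cumulative discharge-ready curves by drug, the difference in 12-hour restricted mean with its 95% CI, and the percentage admitted per drug.

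The cost is revised analysis wording and ED disposition taken from charts that the research specialist already views. No new patients or visits are needed. The downside is that the summary becomes a restricted mean or a curve, not a simple mean stay. Because the drug is the physician's choice, a difference in admissions could reflect which patients received which drug, and this change does not remove that confounding.

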**Research Design:**

Patients presenting with a chief complaint of vomiting and abdominal pain will be screened by the bedside provider for the diagnosis of cyclic vomiting or cannabis induced vomiting syndrome. Per the doctor's choice, 2.5mg droperidol, 5mg haloperidol or 8mg odansteron will be administered. The remaining portion of the patients care is at the discretion of the treating provider including the use of fluids, laboratory diagnostics and radiographic diagnosis and pain medications. The research specialist will be notified when the drugs are administered and view the patient's chart to determine if the reason for the anti-nausea drug was a diagnosis of cyclic vomiting syndrome. If so, the patient's nurse will be messaged via EPIC to inquire on the patient's pain and nausea scores initially versus two hours after the drug is administered, if at the St. Joseph ED, research specialist will make contact with the patient and ask pain/nausea scores at baseline and 2 hours later themselves. Our research specialist will contact patients 1 and 2 days following treatment and enter responses into the project spreadsheet housed on Spectrum Health Lakeland servers. The provider may, at any time choose to add additional anti emetics at their choice but this will be considered as a "rescue" medication for the purposes of this study. All enrolled patients will be added to a study list where the medication given as well as the the secondary outcomes will be recorded on a secure spreadsheet for analysis later.

Continuous variables (such as pain and nausea score, length of stay in the ED will be analyzed using 2 tailed student t-tests. Qualitative variables (number with 2 point improvement in abd pain and nausea score, discharge state at 2 hours, need for rescue anti-emetic, return to ED) will be analyzed using chi-squared analysis.

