**Title:** A comparison of haloperidol 5mg IM vs droperidol 2.5mg and ondansetron for the treatment of hyperemesis in cyclic vomiting syndrome

**NCT#:** NCT05065567

**Date:** 5/19/2025

**Introduction or Background:** Over the past 5 years there has been a 609% increase in persistent vomiting (cyclic vomiting syndrome) related hospitalizations. Many of these have been associated with cannabis use. Despite this significant increase in frequency there is scant literature on the most effective treatment of this condition. A variety of acceptable treatments include ondansetron (Zofran), haloperidol (Haldol) and droperidol. A recent study by Ruberto et al found haloperidol superior to ondansetron for treatment of this condition. Droperidol, a similar D2 agent like haloperidol has been widely used as another treatment option for cyclic vomiting. To date, the two agents have not been compared to determine superiority in managing the symptoms related to cyclic vomiting.

**Problem and Purpose Statement-** The purpose of this study is to compare two commonly used agents for the treatment of cyclic vomiting to see if one agent is inferior to the other in time to improvement in symptoms, need for repeat or rescue medications, treatment failures and complications/side effects. To date, no head to head studies have been published with these two agents.

**Research Questions or Hypothesis:** Is droperidol or haloperidol inferior to the other agent in reducing symptoms related to cyclic vomiting.

**Theoretical Framework-Present Knowledge:** In a recent head to head study, Ruberto et al found that Haloperidol was superior to ondansetron (difference 2.3 cm [95% confidence interval 0.6 to 4.0 cm]; P=.01), with similar improvements in both pain and nausea, as well as less use of rescue antiemetics (31% versus 59%; difference -28% [95% confidence interval -61% to 13%]) and shorter time to emergency department (ED) departure (3.1 hours [SD 1.7] versus 5.6 hours [SD 4.5]; difference 2.5 hours [95% confidence interval 0.1 to 5.0 hours]; P=.03). Haldol, a D2 receptor antagonist, is thought to help suppress the nausea centers of the brain and reduce symptoms from cyclic vomiting. Droperidol, also a D2 antagonist is theorized to have a similar effect. Droperidol has been noted to possibly have a faster time of onset than haloperidol and droperidol is routinely used IV while haloperidol is typically a IM injection.

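### Drug is assigned by physician's choice and compared only with unadjusted tests, with no limit on the comparative conclusion, so patient selection can be reported as a drug effect or can hide one

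*Combined protocol and SAP*

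**What the plan says.** The research question is "Is droperidol or haloperidol inferior to the other agent in reducing symptoms related to cyclic vomiting". Methodology describes the study thus: "This is a clinical trial that will enroll approximately 100 subjects from three different research sites". Both Methodology and Research Design leave the drug to the physician: "Per the doctor's choice, 2.5mg droperidol, 5mg haloperidol or 8mg odansteron will be administered". Randomisation, matching and stratification are not mentioned.

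The primary outcome in Methodology is a change: "Primary outcome will be change in pain and nausea at 2 hrs using a visual analog scale of 0-10".

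Tests are named in two places:
- **Research Design, last paragraph:** "Continuous variables (such as pain and nausea score, length of stay in the ED will be analyzed using 2 tailed student t-tests". Chi-squared is given for four items. The first is "Qualitative variables (number with 2 point improvement in abd pain and nausea score"; the others are discharge state at 2 hours, rescue antiemetic and return to the ED.
- **Statistical Analyses:** ANOVAs of baseline against 2 hours for the three drugs, described in the past tense. Means and SDs of baseline and 2-hour pain and nausea are reported by arm.

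Neither place names a covariate or a site term. Ethical Considerations hopes that the results will inform how these patients are treated in future. No section names confounding as a limitation.

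**The concern.** When the treating physician picks the drug, the groups can differ in severity, in site and in other care, which Research Design also leaves to the provider and which includes pain medication. An unadjusted comparison attributes any resulting difference in outcome to the drug. The error can run either way, so a null result is no safer than a positive one.

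Subtracting baseline helps only in part. It removes a severity gap that is stable over time. It does not remove regression to the mean if physicians chose on the score as observed. Discharge-readiness, rescue use, length of stay and return to the ED subtract no baseline at all.

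The tested quantity is also unsettled. Methodology names change, Research Design names the scores, and the ANOVA sentence can be read as a within-drug test, which would not compare drugs. At stake is whether the study's central comparison can bear the use intended for it.

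**Working it through.** **The plan's own figure.** The only design number is about 100 patients. No alpha, power, effect size, SD or allocation ratio is given, so it cannot be reproduced. Equal thirds give 100/3, or about 33 per arm.

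**Assumed inputs, none from the documents.** No true drug effect; two drugs with 33 patients each; SD σ = 2.5 at both times; baseline-to-2-hour correlation ρ from 0.2 to 0.7; two-sided 5% test; normal scores, not cut off at 0 and 10.

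**Two sources of a baseline gap.** Let s be the gap that arises because choice followed the observed score, and g a gap in severity that is stable over time.
- Baseline gap = s + g
- Expected 2-hour gap = ρs + g
- Gap in change = (ρs + g) − (s + g) = −(1 − ρ)s
- Gap adjusted for baseline = (ρs + g) − ρ(s + g) = (1 − ρ)g

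The change score is biased only by s, and the adjusted model only by g.

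**Change-score test, s = 1, g = 0.** The standard error is σ√(2(1 − ρ)) × √(2/33). At ρ = 0.5 this is 2.5 × 0.246 = 0.615. The bias is 0.5, so the noncentrality is 0.5/0.615 = 0.81, and the noncentral t with 64 df rejects in 12.6% of trials. The change-score column for s = 1 below is exact. The other columns are simulated with 20,000 trials per setting; at ρ = 0.2 the last column shows the spread between repeat runs.

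| ρ | Size of bias | Change, s = 1 | Adjusted, s = 1 | Change, g = 1 | Adjusted, g = 1 |
|---|---|---|---|---|---|
| 0.2 | 0.8 | 17.3% | 5% | 5% | 24–25% |
| 0.3 | 0.7 | 15.7% | 5% | 5% | 21% |
| 0.5 | 0.5 | 12.6% | 5% | 5% | 15% |
| 0.7 | 0.3 | 9.5% | 5% | 5% | 10% |

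The bias column applies to whichever analysis is biased in that scenario: change when s = 1, adjusted when g = 1.

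**Sensitivity (exact, s = 1).** With SD from 2 to 3 over the same correlations, the change-score rate runs from 8.1% to 24.4%. A three-group ANOVA on change with one arm 1 point higher (SD 2.5, simulated) gives 15.1%, 11.7% and 8.9% at ρ = 0.3, 0.5 and 0.7.

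**If the t-test is on the 2-hour score itself.** The gap is ρs + g. The false-positive rate is 6.2% to 20.2% with s = 1, and 36.0% with g = 1.

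**A balanced table is not reassurance.** Take s = 1 and g = −1. The mean baseline gap is zero, and both estimates equal −(1 − ρ), that is −0.8 to −0.3. They agree and both are wrong, with false-positive rates of about 10% to 17% (change) and about 10% to 25% (adjusted).

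**The case against.** **The primary outcome is already change from baseline.** This carries real weight. If severity gaps are stable, change is unbiased and the adjusted model is the one that misleads. The document gives some reason to think so. The research specialist is notified once the drug is given, and only then are scores sought, so the physician may not have acted on the recorded score. But an initial score could have been charted before dosing, so selection on the observed score is not excluded. The outcomes with no baseline to subtract are unprotected in any case.

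**The design is stated openly.** Physician's choice is plain in two sections, no section claims randomisation, and a clinical trial need not be randomised. This stands as far as disclosure goes. The missing part is any limit on the conclusion.

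**The baseline table would show an imbalance.** It would show a difference in mean severity, but the plan takes no step in response, and the opposite-sign case above leaves no trace in it.

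**Not every listed outcome has a test.** Treatment success, defined as "Treatment success = both abdominal pain and nausea score < 2 at 2, 24 and 48 hours", is absent from the chi-squared list, so no error rate is claimed for it here.

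**Stronger readings to avoid.** A reader might infer that the groups did differ, that drug choice varied by site, or that adjustment would cure the problem. No section reports an imbalance or links drug choice to site, and the table shows that adjustment can itself be the biased analysis. Nor should disagreement between the two analyses bar a conclusion. With no confounding and a true effect of 1 to 1.5 points, simulation under the same assumptions had them disagree on significance in about 7% to 27% of trials.

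**Conclusion.** The concern holds as a statement of what can happen. Allocation is by choice, every named test is unadjusted, and the comparative conclusion carries no limitation. Under the assumptions above, a 1-point baseline gap with no drug effect produces a spurious difference of 0.3 to 0.8 points in whichever analysis is biased. False positives are 9.5% to 17.3% for change if choice followed the observed score, and about 10% to 25% for the adjusted model if the gap is stable; the other analysis stays at 5% in each case. The documents do not show which mechanism applied, and the two estimates need not bracket the truth. The structural point rests on the text alone and is firm; the sizes are illustrative. The limit on the conclusion must be added. The adjusted model is supporting evidence, not a remedy.

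**What to change.** 1. **Label and limitations.** Describe the study and its conclusion as a non-randomised, observational comparison. State as limitations confounding by indication, discretionary co-treatment, and baseline scores possibly recorded after dosing.
2. **One primary test.** Reconcile Research Design with Statistical Analyses. State that the primary analysis compares drugs on change at 2 hours, for nausea and pain separately, with one named test: for example a three-group ANOVA on change, with the droperidol-minus-haloperidol difference and its 95% CI.
3. **Sensitivity analysis.** Beside it, report drug differences with 95% CIs from a linear model of the 2-hour score on drug, baseline nausea, baseline pain and site. Label it post hoc, because the ANOVAs are described as already conducted. Where event counts allow, do the same for secondary outcomes with a model suited to each; return to the ED is a count in Methodology but is treated as qualitative in Research Design. Report both results. Do not read their agreement, or a balanced baseline table, as evidence of no confounding, and do not withhold a conclusion merely because one interval excludes zero and the other does not.
4. **Baseline table.** Add site by drug.

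**Cost.** Wording, one extra model per outcome and one table row. Baseline scores are already collected; site is not listed among the recorded items but should be recoverable. The model uses a few degrees of freedom, carries a post hoc label, and may not be feasible for rare outcomes. The conclusion becomes more cautious.

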#### **Ethical Considerations:**

Risks (current and potential).: As all three are standard care the risks are limited to the usual risks associated with treating this condition to include standard medicine reactions, somnolence and dystonic reaction (known with D2 antagonists) and possible QT prolongation (known in all 3 medications). Patients will receive standard care for any side effects of medicine as per standard practice of Emergency Medicine.

**Potential benefits** to the group or class from which the subjects are recruited. Potential benefits to society.

Droperidol has not been commonly used in our emergency departments in the past and if this medicine works better than the others then these patients could experience decreased length of stay and improved time to improvement of symptoms. It is our hope that this project could help guide treatment for this group of patients in the future.

The risk/benefit ratio remains the same whether patients are participating in this study or not. Our clinicians would be using these medicines to treat cyclic vomiting. By formally evaluating response we hope to provide better feedback to physicians going forward with regard to the relative utility of these medicines

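### Patients of one physician may share both drug and outcome, but the planned t-tests, chi-squared tests and ANOVAs treat all of the roughly 100 patients as independent, so the type I error can exceed its nominal level.

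*Combined protocol and SAP*

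**What the plan says.** Under Research Design, treatment is not randomised: "Per the doctor's choice, 2.5mg droperidol, 5mg haloperidol or 8mg odansteron will be administered". The same section adds that "The remaining portion of the patients care is at the discretion of the treating provider", and on rescue, "The provider may, at any time choose to add additional anti emetics at their choice". Under Methodology, one secondary outcome is "Deemed discharge-ready at 2 hours in the opinion of the treating physician". The primary outcome is scored by the patient: "Primary outcome will be change in pain and nausea at 2 hrs using a visual analog scale of 0-10".

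The analysis paragraph of Research Design assigns continuous variables to t-tests ("length of stay in the ED will be analyzed using 2 tailed student t-tests") and binary variables to chi-squared tests. The Statistical Analyses paragraph, which sits under Informed consent, reports that "ANOVAs were conducted to determine whether significant differences existed between baseline and 2 hours after drug administration for the three drugs". Neither place mentions physician, site, clustering, a mixed model or robust standard errors. Methodology gives about 100 subjects and three sites. The documents give no alpha, no number of treating physicians and no figure for prescribing preference or within-physician correlation. The study list described in Research Design holds the medication given and the secondary outcomes. Physician is not named among its fields.

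**The concern.** A t-test, chi-squared test or ANOVA on individual patients assumes that each patient brings independent information about the drug. Here one person picks the drug and also drives several outcomes. If physicians have favourite drugs, part of the drug comparison is a comparison between physicians. If physicians also differ in how readily they give rescue, call a patient ready or send a patient home, the plain standard error leaves that variation out and is too small. A few prescribers' habits could then pass for a drug effect.

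Uneven uptake of one drug is plausible, because Ethical Considerations says "Droperidol has not been commonly used in our emergency departments in the past". This is a different matter from imbalance in patient severity: with severity perfectly balanced, the standard errors could still be too small.

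**Working it through.** **Inputs from the documents.** About 100 patients, three drugs, physician's choice, two-tailed tests, no grouping term. There is no stated alpha or sample-size derivation to reproduce.

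**Assumed inputs.**
- Nominal alpha 5%, two-sided.
- 10 to 50 physicians (J).
- Within-physician outcome correlation (ICC) 0 to 0.20.
- Drug habit: with probability p the physician gives a favourite drug, otherwise one of the three at random. The favourite's share is p + (1 − p)/3: p = 0.8 gives 0.8 + 0.067 = 87%; p = 0.5 gives 0.5 + 0.167 = 67%; p = 0 gives 33%, which is no preference.
- A 40% event rate for binary outcomes.

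**Analytic approximation.** With m = 100/J patients per physician, the variance of a drug difference is inflated by about

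DE = 1 + (m − 1) × ICC × p²,

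where p² is the share of variation in drug use that lies between physicians. The true error is 2 × [1 − Φ(1.96/√DE)]. Since ICC and p² multiply, DE is 1 if either is zero.

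- 10 physicians, p = 1, ICC 0.05: DE = 1 + 9 × 0.05 = 1.45; error 10.4% (simulated 10.7%).
- 12 physicians, p = 0.8, ICC 0.20: m = 8.33; DE = 1 + 7.33 × 0.20 × 0.64 = 1.94; 1.96/1.39 = 1.41; error about 16% (simulated 15.6%).
- 40 physicians, p = 0.8, ICC 0.05: m = 2.5; DE = 1 + 1.5 × 0.05 × 0.64 = 1.048; error about 5.5% (simulated 5.9%).

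The simulation lets caseloads vary by chance, so it can run a little above the equal-caseload formula.

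**Simulation with no true drug effect.** Rejection rate (%) at nominal 5%; the t-test and chi-squared compare two drugs, the ANOVA all three. There were 20,000 runs per row, and 6,000 for the 12-physician rows.

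| Physicians | Favourite share | ICC | t-test | ANOVA | Chi-squared |
|---|---|---|---|---|---|
| 10 | 33% | 0.20 | 4.9 | 5.2 | 5.1 |
| 10 | 100% | 0 | 5.1 | 5.1 | 5.2 |
| 40 | 67% | 0.05 | 5.2 | 5.4 | 5.1 |
| 40 | 87% | 0.05 | 5.9 | 5.9 | 5.8 |
| 40 | 87% | 0.20 | 8.8 | 10.3 | 7.5 |
| 20 | 67% | 0.05 | 5.2 | 5.9 | 5.5 |
| 20 | 87% | 0.05 | 7.0 | 7.6 | 6.3 |
| 20 | 87% | 0.20 | 11.8 | 15.1 | 9.8 |
| 12 | 87% | 0.05 | 8.6 | 9.8 | – |
| 12 | 87% | 0.20 | 15.6 | 22.4 | – |

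The first two rows show that preference alone, or correlation alone, leaves all three tests near 5%. For chi-squared with 12 physicians and an 87% share, a separate run with physician SD 0.5 to 1.2 on the logit scale gave 8 to 18%.

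**Do the remedies work?** A random-intercept model (300 runs per setting; 20 physicians at ICC 0.10 and 0.20, 30 at 0.20) rejected 3 to 4%, against 10 to 11% for the t-test in the same runs. Logistic models with physician-clustered errors (1,500 runs, 87% share) rejected 5 to 6% with 20 to 30 physicians and 7 to 8% with 12.

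**The case against.** The strongest reply is that both conditions are inferred. The documents say that the doctor chooses, not that each doctor has a habit. They say droperidol was uncommon in the past, not that a few early users give it now. The Informed consent section expects clinicians to try it anyway, which is compatible with broad uptake. Twelve physicians over three sites is four per site, and 0.20 is the top of the assumed correlation range. All of this stands, and it means the high figures are only possible values.

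A reader might infer that the error rate does exceed 5%, and does so for every planned test. The documents do not support that. Without preference or without correlation the rate stays near 5%, and the documents report neither. The primary outcome is the patient's own score, collected by a nurse or research specialist, so within-physician correlation is less certain there. It is not ruled out, because pain medication and added antiemetics within the two hours are at the provider's discretion.

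A further reply is that the main threat from physician choice is bias from who receives which drug, and clustered errors do not remove it. That is correct, and it limits what the change can achieve. It does not make the independence assumption safe.

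**Conclusion.** The omission is documented: physician choice runs through treatment and several outcomes, and no planned test allows for it. The consequence is conditional. If physicians differ in drug preference and outcomes correlate within physician, the true type I error can exceed an assumed 5%. For the t-test it is about 5 to 9% with 40 or more physicians, or with weaker preference and correlation. It reaches about 16%, and 22% for the ANOVA, with 12 physicians, an 87% favourite share and ICC 0.20. Physician number, preference, correlation and alpha are all assumptions, so the actual inflation cannot be calculated from the documents. Concern is greatest for rescue, discharge readiness and length of stay. This is a cheap improvement worth making, separate from confounding.

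**What to change.** - **Data.** Add a coded ID for the treating physician, and the site, to the study spreadsheet. If collection is complete, as the past tense in Statistical Analyses suggests, take them from the chart.
- **Continuous outcomes.** For the 2-hour change in pain and in nausea, and for length of stay, replace the t-tests and ANOVAs with a linear mixed model. Drug and site are fixed effects, physician is a random intercept, and degrees of freedom are small-sample. For the scores, add the baseline score as a fixed effect, so that change from baseline remains the outcome. Site is needed also because a research specialist collects scores in person at one named ED, while elsewhere the nurse is messaged.
- **Binary outcomes.** For rescue, discharge readiness and return to ED, replace chi-squared with logistic models using physician-clustered standard errors and a small-sample correction.
- **Reporting.** Give the number of physicians per drug and each coded physician's drug split, so readers can judge how far drug and physician overlap.

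The cost is two fields, possible chart extraction, and somewhat wider confidence intervals. With about 12 physicians the clustered logistic test may still run slightly above 5%. None of this removes confounding by the physician's choice of drug, and the report should say so.
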